		reminder that the mid-point survey was intended to facilitate a continuing consent discussion in section 21.0 and 22.3 per IRB comments (moved from 21.2 to 21.0).	
9	5.3	Clarifying section 9.3 to make the where how and why clear	No
10	5.4	Updated sections 9, 21, & 22 to affirm that patient recruitment methods are approved by CM	No
11	5.5	
Updated Garmin Health App title to Garmin Connect app for accuracy in sections 5, 6.3, 12, 23.2, 26, and 32
 
Updated sections 5, 12 and 26 to clarify that data from the Garmin Connect app will be uploaded by the Garmin Health API developed by Children's Mercy Research Informatics.
 
Updated sections 26 and 29.1 to specify that a copy of data will be kept in the diabetes data mart (D-dock), used for CGM uploads, and clarified that data collection would be completed by the diabetes data mart developed by CMH.
 
Also updated ICF to better reflect data collected, privacy statements, account status after study completion, etc. Per IRB comments. Added in a clarification that the Glooko and Dexcom apps will only be used for data collection if the participant uses the apps.
	Yes
12	5.6	Added language to section 9.3 to include the recruitment flyer in CM Find a Study	
13	6.0	Added in payment for completing surveys to section 18. Updated Garmin Connect wording in the information letter to current edition. And added insurance type as information collected to sections 23 and 26 and the information letter	Yes
14	6.1	
Updated section 9.3 to include putting the study flyer in the clinic intake form
 
Updated sections 26 & 29 to clarify that the Diabetes Data Mart (or RTDA Data Warehouse) is the Diabetes Data Dock
	Yes

SHORT TITLE: Garmin PACT

		
And 29.1 & 23.3 to clarify data will be kept in the CMH Microsoft Azure Cloud which includes Sharepoint (originally stated as the drive), and will be stored per CM policy
 
Corrected the payment schedule in the information letter
 
Added in the CCPay handout for participant knowledge
	
15		
Updated Section 5 Study Calendar to make study visits approximately the days stated in the protocol. Updated section 5.0 and 12 to make it clear any additional visits to troubleshoot Garmin issues will occur at Visit 2, Visit 3 and Visit 4 (approximately at days 14, 28, 56).
	Yes
16		
Updated sections 23 to correctly document that the study database isn't only in the Onedrive/ Microsoft Teams
 
Updated information letters to clarify the study objectives
	Yes
17		
Updated section 9.3, 24, and 26 to include the Health Device Portal texting system in communication.
 
Updated section 21.4 to clarify how to handle data collection during and after the reconsent of a participant who turns 18.
 
Updated section 23.3 to remove language about study coding study information with a study ID, as this is incorrect. Added in that the prescreening/ enrollment log and study data sheets are kept together in the study database.
 
Updated section titles in section 26 to make it clear data is collected from both child and adult participants. Also removed language about coded data from section 26. Also updated language about parent demographics data including T1D information, as this is incorrect (includes data such as shipping information for sending Garmins which was added to the child/ adult participant section as well).
	
18		Clarified the sections 21, 21.2, 27.2 on consent/ assent, because following the P/A/C	

		
policy with a waiver of documentation of assent/ consent would not be a telephone consent as stated in the P/A/C policy we cited. However, we state we waive assent/ consent but perform telephone consents.
 
Also updated section 22.4 and 27.2 to remove the titles/ numbers of policies to ensure outdated/ renamed policies are not being cited.
 
Updated section 32 to include electronic (email, text) communication in the consent discussion.
	
19		Updated section 6.4 to allow participants to keep Garmins when they withdraw, and allow evaluating participants when they lose/ break a Garmin more than two times to see if they should be allowed more replacement Garmins.	No
20		Corrected protocol section 25 to note that participants may be lost to follow up if they are actively contacted three times, which does not include contacts like automatic text alerts.	No

Key Words: Type 1 diabetes (T1D), youth, physical activity monitors, HbA1c

Table of Contents

STUDY INFORMATION

- [1.0 Study Summary](#)
- [2.0 Objectives](#)
- [3.0 Background](#)
- [4.0 Study Endpoints](#)
- [5.0 Study Design](#)
- [6.0 Study Interventions](#)

PARTICIPANT MANAGEMENT

- [7.0 Inclusion and Exclusion Criteria](#)
- [8.0 Local Number of Participants](#)
- [9.0 Screening and Recruitment Methods](#)

Primary Objectives	
Measure physical activity and sleep for up to 365 days using a Garmin physical activity tracker among youth and young adults with T1D.
 
Evaluate the impact of physical activity and sleep related variables on rate of DKA admission over 90 and 180, and 365 ± 30 days
 
Evaluate the impact of physical activity and sleep related variables on change in Time in Range (TIR) and other continuous glucose monitor-derived metrics of glycemic control over 90, 180, and 365 ± 30 days
 
Test the impact of physical activity and sleep related variables on machine learning models to predict change in HbA1c, DKA admissions, and change in Time in Range over 90, 180, and 365 ± 30 days

Secondary Objectives	
Examine for correlations between self-reported physical activity (IPAQ), hypoglycemia fear (HFS-II), and parent hypoglycemia fear (HFS-P) at 0, 6, and 12 months after study enrollment.
 
Evaluate any change in physical activity levels via self-report with the IPAQ survey (to allow comparisons to external cohorts).
 
Evaluate any change in how participants feel about episodes of hypoglycemia while wearing the Garmin physical activity tracker via the Hypoglycemic Fear Scale II (HFS-II)
 
Evaluate any change in how parents feel about episodes of hypoglycemia in their children wearing the Garmin physical activity tracker via the Hypoglycemic Fear Scale II for Parents (HFS-P)

Research Intervention(s)/	Garmin physical activity tracker

Investigational Agent(s)	
IND/IDE #	NA
Study Population	Youth (8-21 YO) diagnosed with T1D and parents of youth (8-17 YO)
Sample Size	1000 pre-screened for total enrollment goal of 300 (200 youth 100 parents)
Study Duration for Individual Participants	365 Days (\pm 30 days)
Study Specific Abbreviations/ Definitions	T1D = Type 1 diabetes DKA= Diabetic Ketoacidosis IPAQ=International Physical Activity Questionnaire HFS-II=Hypoglycemic Fear Scale II HFS-P= Hypoglycemic Fear Scale II for Parents HbA1c= Hemoglobin A1c

2.0 Objectives*

2.1 Primary Objectives:

1. Measure physical activity and sleep for up to 365 (\pm 30 days) days using a Garmin physical activity tracker among youth and young adults with T1D.
2. Evaluate the impact of physical activity and sleep related variables on rate of DKA admission over 90 and 180, and 365 \pm 30 days
3. Evaluate the impact of physical activity and sleep related variables on change in Time in Range and other continuous glucose monitor-derived metrics of glycemic control over 90, 180, and 365 \pm 30 days
4. Test the impact of physical activity and sleep related variables on machine learning models to predict change in HbA1c, DKA admissions, and change in Time in Range over 90, 180 and 365 \pm 30 days

2.2 Secondary Objectives:

1. Examine for correlations between self-reported physical activity (IPAQ), hypoglycemia fear (HFS-II), and parent hypoglycemia fear (HFS-P) at 0, 6, and 12 months after study enrollment.
2. Evaluate any change in physical activity levels via self-report with the IPAQ survey (to allow comparisons to external cohorts).
3. Evaluate any change in how participants feel about episodes of hypoglycemia while wearing the Garmin physical activity tracker via the Hypoglycemic Fear Scale II (HFS-II)
4. Evaluate any change in how parents feel about episodes of hypoglycemia in their children wearing the Garmin physical activity tracker via the Hypoglycemic Fear Scale II for Parents (HFS-P)

3.0 Background*

3.1 Physical activity is an important aspect of Type 1 Diabetes (T1D) management. However, very little investigation has specifically targeted the use of physical activity monitors in T1D management in youth. In a recent literature review of physical activity research using wearable devices in T1D, only three studies have been identified, all since 2019. It is important to establish the utility of physical activity trackers in T1D to identify patients who would benefit from interventions to increase physical activity.

There is also interest in predicting clinical outcomes like future glycemic control, hospitalization, mental health, etc. No studies have examined the utility of physical activity data from wearable devices in making such predictions.

3.2 Small studies have shown that it is feasible for people with T1D to wear physical activity trackers in non-clinical settings, and the devices show accuracy (Cescon et al., 2021). Additionally, T1D adolescents (7-19 Y.O.) can wear physical activity trackers while recording diet, although in this study the minimum device use time was three days (Jaggers et al., 2021). Physical activity trackers have also been used to study mealtime glucose control (Ozaslan, Patek, & Breton, 2020). Overall, there is support in the literature for the use of physical activity trackers in T1D management.

3.3 There is a need for accurate and timely record of longitudinal physical activity which affects the overall health of youth (8-21 Y.O.) with T1D (variables include DKA admissions, time in range, HbA1c, etc.). It is necessary to confirm the feasibility and utility of physical activity trackers for predicting near-term T1d outcomes. This study builds on previous studies that establish the feasibility of tracking physical activity and T1D and the accuracy of such devices for doing so.

4.0 Study Endpoints

1. Minutes/day of Moderate-to-vigorous physical activity (MVPA) – from Garmin device over 30, 90, 180, and 365 ± 30 days
2. Sleep minutes/day – derived from Garmin device over 30, 90, 180, and 365 ± 30 days
3. Other activity metrics derived from Garmin device over 30, 90, 180, and 365 ± 30 days
4. HbA1c – collected from Electronic Medical Record, obtained via standard care (binned as 46-135 days, 136-225 days, 226-305 days, and 306-410 days)
5. Hospital admissions for DKA (0-180 days and $181-365 \pm 30$ days)
6. 14-day Time in Range and other CGM-derived metrics of the quality of glycemic control over 30, 90, 180, and 365 ± 30 days
7. Model performance characteristics (e.g. precision, recall, F1) of predictive models for the outcomes listed in 4.1-4.6

5.0 Study Design*Participants with T1D treated at the Children's Mercy Endocrine clinic aged 8-21 years old will be asked to wear a Garmin VivoSmart 4 (or later) physical activity tracker for at least 6 months. This tracker will collect detailed physical activity and sleep data as measured by moderate to vigorous physical activity (MVPA) and sleep minutes/day. The tracker collects heart rate and accelerometry data, collected into the Garmin Connect application. The diabetes center will use the Garmin Health API connection developed by Children's Mercy Research Informatics to extract the data into a data warehouse in Microsoft Azure (CMH account). As noted in previous studies, MVPA is automatically measured by the tracker when the wearer runs for >1 minute or walks for >10 consecutive minutes. The weekly MVPA and step count are both weighted by multiplying the mean of weekday activity by 5, adding it to the mean of weekend activity and dividing the sum by 7.

$$\text{Weighted MVPA} = \frac{[(\text{MVPA}) \times 5] + (\text{MWVPA})}{7}$$

$$\text{Weighted step count} = \frac{[(\text{MSC}) \times 5] + (\text{MSC weekend})}{7}$$

If the subject wears the tracker for >8 hours between 9 AM and 9 PM, the day is used in the weighing calculation (Grimes et al., 2022). Clinical data will be collected from the medical record and coded (labeled with the study ID to minimize use of personal data). Also, self-reported personal health will be collected from the CMH-approved vendor software to which they upload their self-management device data. Baseline and end of study surveys including International Physical Activity Questionnaire (IPAQ), the Hypoglycemic Fear Scale II (HFS-II) for participants, and Hypoglycemic Fear Scale for parents (HFS-P) will be collected from participants/ parents. Surveys will be given to participants based on their ages and the ages surveys are validated for.

Table of Events:

	Pre-screening (Pre-consent)	Visit 1 Day 1 app x.	Visit 2 ^a Day 14 appx. (PRN)	Visit 3 ^a Day 28 appx. (PRN)	Visit 4 ^a Day 56 appx. (PRN)	Visit 5 Day 180 appx.	Visit 6 Day 365 appx.	Unscheduled Visit
EMR Review Eligibility	X							
Verbal Consent		X						
Demographics		X						
Clinical history ^b		X					X	
Send Garmin tracker		X						
Surveys ^c		X				X	X	
Mid-Study Check-In Survey						X		
Garmin Troubleshooting Visits			X	X	X			

- a. Additional virtual or in person visits may be scheduled at Visit 2, Visit 3, and Visit 4 as needed for device troubleshooting and additional education, depending on the needs of the subjects
- b. A1c will be drawn SOC as a part of the clinical history, in the absence of A1c results, GMI will be deduced from CGM data
- c. The IPAQ (for >15 YO) and HFS-P/HFS-II (HFS-II child for 11-18 Y.O., HFS-II adult for >18 YO)

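### Endpoint 7 as worded does not by itself answer primary Objective 4: its outcome list includes the predictors, its example metrics need an unstated cut-off for HbA1c and Time in Range, and it states no comparison with and without Garmin variables

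*Combined protocol and SAP*

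**What the plan says.** Section 2.1, item 4, a primary objective, is to "Test the impact of physical activity and sleep related variables on machine learning models to predict change in HbA1c, DKA admissions". Its third target is TIR change, and the horizons it names are days 90, 180 and 365, with a 30-day margin.

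Section 4.0, item 7, is the only endpoint about prediction: "Model performance characteristics (e.g. precision, recall, F1) of predictive models for the outcomes listed in 4.1-4.6".

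The items it points to are these:

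- 4.1 is daily moderate-to-vigorous activity from the device.
- 4.2 is "Sleep minutes/day".
- 4.3 is "Other activity metrics derived from Garmin device over 30, 90, 180, and 365 ± 30 days".
- 4.4 is HbA1c from routine care, "binned as 46-135 days, 136-225 days, 226-305 days, and 306-410 days".
- 4.5 is hospital admission for DKA, over days 0-180 and 181-365 ± 30.
- 4.6 is 14-day TIR and other CGM metrics at 30, 90, 180 and 365 ± 30 days.

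The only comparison in the available statistical section (28.1) is between participants and a propensity-matched cohort, where possible. Section 3.1 motivates the study by noting that wearable activity data have not been examined for this kind of prediction.

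**The concern.** The impact of a set of variables on a model is a difference: how well the model predicts with them, less how well it predicts without them. Endpoint 7 names the performance of models and stops there. A model could predict well from baseline HbA1c and diabetes history alone, and a single performance figure would not show whether the Garmin data had added anything.

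Two features of the wording make this worse. The outcome list runs from 4.1, so it takes in the activity and sleep measures themselves. The metrics offered as examples are classification metrics, while most of the listed outcomes are continuous. If no cut-off is fixed in advance, it can be chosen after the data are seen, and the reported figure depends heavily on that choice.

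**Working it through.** The plan gives no performance target, power or sample-size derivation for Endpoint 7, so there is no stated figure to reproduce. The check has two parts.

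**1. The endpoint list set against Objective 4**

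| Item | Scale | Role in Objective 4 |
|---|---|---|
| 4.1 activity minutes | continuous | predictor |
| 4.2 sleep minutes | continuous | predictor |
| 4.3 other Garmin metrics | essentially continuous | predictor |
| 4.4 HbA1c | continuous, listed as a value | target, but as change |
| 4.5 DKA admission | event | target; no 90-day window |
| 4.6 TIR and CGM metrics | continuous, listed as a value | target, but as change |

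Three of the six items are Objective 4's predictors and three are its target domains. Five of the six are essentially continuous. The HbA1c bins are windows in days, not outcome classes. The only HbA1c threshold in the documents, a predicted rise of 0.3 points (section 9.3), is a recruitment route and is not tied to Endpoint 7. The matched cohort in 28.1 contrasts groups of people, not sets of predictors.

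**2. How F1 behaves on a cut continuous outcome**

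Every prevalence, R² and DKA rate below is an assumption; none is in the documents.

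*Dependence on the cut-off.* Take a standard normal outcome and a linear score explaining a share R² of its variance. Flag the top fraction p of scores, where p is the prevalence of the class. Then F1 = 2·TP / (flagged + events). Simulation with 2 million draws gives:

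| Prevalence p | R² = 0.20 | R² = 0.25 | R² = 0.30 | All labelled positive, 2p/(1+p) |
|---|---|---|---|---|
| 10% | 0.293 | 0.326 | 0.354 | 0.182 |
| 20% | 0.406 | 0.435 | 0.465 | 0.333 |
| 30% | 0.496 | 0.523 | 0.547 | 0.462 |
| 40% | 0.575 | 0.598 | 0.620 | 0.571 |
| 50% | 0.648 | 0.667 | 0.684 | 0.667 |

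At R² = 0.25, moving only the cut-off shifts F1 by 0.667 − 0.326 = 0.341. At 30% prevalence, raising R² from 0.20 to 0.25 shifts it by 0.523 − 0.496 = 0.027. At 50% prevalence, the model with R² = 0.25 scores the same F1 as labelling everyone positive.

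*Information lost by cutting.* For a normal outcome and a modest association, relative efficiency is φ(z)²/[p(1−p)]. This is 0.637 for a median split (0.637 × 200 ≈ 127 youth) and 0.490 for a 20/80 split (0.490 × 200 = 98 youth), if all 200 youth contribute an outcome.

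*DKA precision.* The 95% half-width around a recall of 0.6 is 1.96·√(0.6 × 0.4 / events).

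| Assumed DKA rate | Events in 200 | Half-width |
|---|---|---|
| 3% | 6 | ±0.39 |
| 5% | 10 | ±0.30 |
| 10% | 20 | ±0.21 |

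**The case against.** There is a fair case on the other side, and parts of it stand.

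- **The targets are covered.** Items 4.4-4.6 are Objective 4's target domains, and model performance is the quantity that any with/without comparison would use. A reader might infer that Endpoint 7 fails to measure Objective 4 at all. The documents do not support that: the endpoint holds a necessary component and lacks the contrast.
- **The contrast is implied.** Testing the impact of variables on a model suggests comparing models that differ in those variables, and such detail often sits in an analysis section. This stands as a reading of the objective. It does not supply the missing definition, because no available text says what the reference model is or how the difference is measured.
- **The text is incomplete.** The available text ends at 28.1, although the contents list sections up to 35. A reader might infer that the plan contains no such comparison anywhere. That can be said only of Endpoint 7 and the text at hand.
- **The metrics are examples.** A reader might infer that HbA1c and TIR will be scored by F1. The wording leaves other metrics open, and precision and recall suit DKA. What remains is that no continuous-outcome metric and no cut-off is named.
- **The figures are not the trial's.** The documents contain no median or 20/80 split and no 3% DKA rate. The efficiency figures describe estimating an association, not machine-learning performance. Precision reported beside F1 would also expose an all-positive model: at 3% prevalence its precision is 0.03.
- **Forecasting activity is possible.** Items 4.1-4.3 are measured repeatedly, so later activity could be predicted from earlier data. No stated objective asks for this.

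**Conclusion.** The point holds in a limited form. As worded, Endpoint 7 cannot alone show what the Garmin variables add to prediction, which is what primary Objective 4 asks. Three facts carry this, and they rest on the text rather than on the illustrations: half of the listed outcomes are the predictors, no cut-off or continuous metric is given for HbA1c and TIR, and no with/without comparison appears in the available text.

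The size can only be illustrated. Under the assumed normal model, the choice of cut-off moves F1 by about 0.34, against about 0.03 for a five-point gain in R². The direction does not depend on those exact values, but the numbers do. The efficiency and all-positive F1 figures should not be read as losses this study will suffer.

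Two mismatches need settling at the same time. Objective 4 predicts change while 4.4 and 4.6 list values, and it names a 90-day DKA horizon that the windows in 4.5 do not provide.

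**What to change.** Reword Endpoint 7 and add matching text to section 28:

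1. **Outcomes.** Limit it to HbA1c change, DKA admission and TIR change (from 4.4-4.6, restated as changes where needed) at Objective 4's horizons of 90, 180 and 365 ± 30 days. Reconcile the 90-day DKA horizon with the 0-180 and 181-365 ± 30 day windows in 4.5.
2. **Metrics.** For HbA1c and TIR change, use a continuous-outcome metric such as MAE or RMSE, with calibration. For DKA, keep precision and recall type metrics and report them with the prevalence. If a classified version of HbA1c or TIR change is also wanted, fix its cut-off before analysis.
3. **Contrast.** Define the endpoint as the paired difference in out-of-sample performance between models with and without the Garmin activity and sleep variables. Use the same participants and participant-level resampling, and give a confidence interval.

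The cost is wording plus one reference model per outcome, or up to 3 × 3 = 9 extra fits if each horizon is modelled separately. No new data are needed. The drawback is the DKA contrast: with about 6 events in 200 at an assumed 3%, its interval will be very wide. The plan should say in advance that this part is descriptive if events are that few.

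### The weighted MVPA and step-count rule counts the weekend mean once instead of twice, so every weighted value with weekend activity is too low by one seventh of the weekend mean

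*Combined protocol and SAP*

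**What the plan says.** Section 5.0 (Study Design) says that the tracker will "collect detailed physical activity and sleep data as measured by moderate to vigorous physical activity (MVPA) and sleep minutes/day". It then gives one rule for summarising weekly MVPA and step count: "multiplying the mean of weekday activity by 5, adding it to the mean of weekend activity and dividing the sum by 7".

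Two displayed formulas follow, one for MVPA and one for step count. Each multiplies the first term by 5, adds a second term without a multiplier, and divides by 7. The symbols (MVPA, MWVPA, MSC) are not defined.

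The same section admits data one day at a time: if the tracker is worn for more than 8 hours between 9 AM and 9 PM, "the day is used in the weighing calculation".

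Elsewhere, item 1 of Section 4.0 (Study Endpoints) is "Minutes/day of Moderate-to-vigorous physical activity (MVPA" and so on, taken from the device, and the first primary objective in Section 2.1 begins "Measure physical activity and sleep for up to 365". No other section restates or corrects the weighting rule.

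**The concern.** The usual purpose of a 5:2 weighting is to turn a weekday mean and a weekend mean into an average over a seven-day week, even when valid days are unevenly spread. The divisor of 7 shows that this is what was intended. The written rule, however, counts five weekdays and only one weekend day and still divides by seven. A participant who does the same amount every day does not get that amount back.

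The stake is mainly the absolute level of activity. Measuring activity is the first primary objective, and Section 5.0 offers no other summary rule for MVPA. The rule therefore very probably feeds endpoint 1, although no section says so outright.

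Primary objectives 2 to 4 refer only to activity and sleep related variables. They are touched only where the weighted variables are used. Sleep minutes and the IPAQ are not affected.

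**Working it through.** **Inputs.** The multipliers 5 and (implicitly) 1 and the divisor 7 come from Section 5.0. A week has 5 weekdays and 2 weekend days. The plan gives no worked value to reproduce and no activity levels, so the activity levels below are illustrative.

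**Notation.** WD is the mean per weekday and WE the mean per weekend day.

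**Step 1: do the weights sum to 1?**

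- Written rule: (5·WD + WE)/7, with weights 5/7 + 1/7 = 6/7.
- Seven-day average: (5·WD + 2·WE)/7, with weights 5/7 + 2/7 = 1.

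**Step 2: size of the gap.**

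(5·WD + 2·WE)/7 − (5·WD + WE)/7 = WE/7.

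With r = WE/WD, the relative shortfall is WE/(5·WD + 2·WE) = r/(5 + 2r):

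| r | Shortfall |
|---|---|
| 0 | 0% |
| 0.25 | 0.25/5.5 = 4.5% |
| 0.5 | 0.5/6 = 8.3% |
| 1 | 1/7 = 14.3% |
| 1.5 | 1.5/8 = 18.75% |
| 2 | 2/9 = 22.2% |

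**Step 3: worked cases.**

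| WD | WE | Seven-day average | Written rule |
|---|---|---|---|
| 60 min | 60 min | 420/7 = 60.0 | 360/7 = 51.4 |
| 60 min | 120 min | 540/7 = 77.1 | 420/7 = 60.0 |
| 60 min | 0 min | 300/7 = 42.9 | 300/7 = 42.9 |
| 10,000 steps | 10,000 steps | 70,000/7 = 10,000 | 60,000/7 = 8,571 |

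**Step 4: can the ranking of two participants reverse?** Yes.

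- Participant A (WD 30, WE 90): average 330/7 = 47.1, written 240/7 = 34.3.
- Participant B (WD 45, WE 30): average 285/7 = 40.7, written 255/7 = 36.4.

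A is the more active of the two but scores lower.

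**Step 5: how much ordering is lost overall?** Assume that WD and WE are bivariate normal with covariance matrix S (an assumption; the documents give nothing on this). With a = (5, 2)/7 and b = (5, 1)/7, the correlation between the correct and written scores is a′Sb/√(a′Sa · b′Sb). The share of pairs reversed is arccos(correlation)/π. The sevenths cancel.

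- Equal SDs, correlation 0.5: 34.5/√(39 × 31) = 0.992, so about 4.0% of pairs reversed.
- Equal SDs, correlation 0: 27/√(29 × 26) = 0.983, about 5.8%.
- Weekend SD double, correlation 0: 33/√(41 × 29) = 0.957, about 9.4%.

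**Step 6: would another divisor do?** Dividing by 6 makes the weights sum to 1 but does not give a seven-day average: WD 60 and WE 30 would give 330/6 = 55.0 against the true 360/7 = 51.4.

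**The case against.** The strongest defence is that the weekend term is a two-day total. The sentence concerns weekly quantities, and five times a weekday mean plus a weekend total, divided by 7, is a correct daily average. The wear-time rule decides which days count; it does not by itself say whether valid weekend days are averaged or summed. The formula symbols are undefined, so they cannot settle the matter.

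This reading is possible but strained. The sentence uses the word mean for both terms, and the weekday mean must be per day because it is multiplied by 5. Nothing defines a weekend total, and with only one valid weekend day such a total could not be formed directly. Damage in the PDF text is not a likely explanation either, because the prose and both formulas all lack the factor.

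Three further points stand as limits:

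- The link from this rule to endpoint 1 is inferred. Step count is not named among the endpoints, and Section 28.0 as supplied does not mention the weighted variables.
- The documents do not show whether the derivation code follows the written rule. If it already uses 5:2 weights, or sums the weekend days, results are unaffected and only the text is wrong.
- The effect on ordering is modest under the assumed distributions. The reversed pair in Step 4 shows that reversal can happen, not how often.

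**Conclusion.** The rule is wrong as written. With both terms read as means per day, every weighted MVPA or step-count value with any weekend activity is too low by exactly WE/7. That is 14.3% when weekend and weekday activity are equal, and between 8.3% and 22.2% for weekend-to-weekday ratios from 0.5 to 2 (assumed ratios).

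The loss depends on each participant's own weekend pattern, so rescaling the weighted scores by a constant, such as 7/6, does not repair them. The resulting numbers look plausible, so the error could pass unnoticed into reported minutes and steps per day.

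Analyses of association or prediction that use these variables are probably hurt less: the correlation with the correct score is 0.957 to 0.992 in the three assumed cases. The arithmetic is certain. What remains open is whether the code follows the text.

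**What to change.** In Section 5.0, change the sentence and both formulas to [(weekday mean × 5) + (weekend mean × 2)]/7, for MVPA and for step count. Define each symbol and state that both terms are means per valid day. If a two-day weekend total was in fact intended, the text must say so, and the term should not then be called a mean of weekend activity.

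Then check the derivation code against the corrected formula. If it followed the written rule, recompute the stored weighted values from the daily tracker data; the plan already provides to "extract the data into a data warehouse in Microsoft Azure".

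The cost is one sentence, two formulas, the symbol definitions and a code check, plus at most one re-run of the derivation. No new data collection is needed.
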